9.6.3. Description of study procedure(s)

1. Smart Watch (Empatica <https://www.empatica.com/research/e4/>)

After consent, on the patient's initial visit, the patient will be provided and instructed in the use of the Empatica E4 watch. The purpose of the watch will be to track various bio signals in the outpatient environment. These signals will be used to assess how the patient is sleeping prior to the admissions to the hospital for the overnight polysomnography studies.

2. Questionnaires and testing

Questionnaires and tasks that will be used during the study visit (as have been listed in prior sections) are described in more detail below. In addition, a short note is provided on the rationale for their selection.

Sleep inertia is a period of reduced performance and alertness following awakening. This period may be as short as 30 minutes or as long as an hour or more depending on the performance task. For a good quantification of sleep inertia, it is important to do repeat assessments with a high temporal resolution, and as such, the tests used cannot be too long. For DBS in patients with motor symptoms one needs to consider that for a between-stimulation-condition comparison of sleep inertia, tasks with a motor component are probably not best suited to the task, since it will be difficult to differentiate an effect of impaired motor performance from a deficit in alertness.

We have selected an array of measures that have been previously tested and might be applicable in accurately quantifying changes in sleep inertia in our populations of interest.

The Karolinska Sleepiness Scale (KSS, measuring vigilance and lasting a few seconds) also had good sensitivity as does the Psychomotor Vigilance Test (PVT) (Santhi et al 2013).. Finally, we will use the Karolinska Drowsiness Test (KDT) which assesses waking resting EEG, eyes open 1 min; eyes closed 1 min.

3. EEG and polysomnography

Scalp EEG electrodes are individually attached while additional electrodes record EMG, EOG and ECG signals (detecting muscle activity, eye movements and the electrocardiogram respectively). We will also use sensors to monitor breathing parameters such as airflow and respiratory effort and EKG. Video recordings with video being time-locked to the polysomnography EEG data.

4. Autonomic measures:

In addition to data captured with the polysomnography system described above. Systems such as an FDA Empatica E4 watch can be used where available and tolerated. These sensors capture high-resolution data relevant to heart rate and blood pressure.

5. Biological sampling and analyses:

Patients will provide a single salivary sample for cortisol measures upon awakening (6am) on each visit.

6. Other devices and procedures:

Subjects will be wear a “smart” watch, Empatica E4 or Empatica II watch, which are FDA approved device for tracking electrodermal activity (EDA), heart rate (HR), and photoplethysmography (ppg). Participants may also wear a commercially available smart watch, such as the Apple Inc. watch or Fitbit. The patient will already be familiar with their FDA approved patient programmer used with their DBS device from prior clinic visits, as well as instructions and advice offered during their hospital stay. This tablet-like or pager-like device allows for adjustment of stimulation settings (amplitude, pulse width and frequency) by its operator, by communicating wirelessly with the implanted battery and DBS system.

Prior to both epilepsy monitoring unit (EMU) stays in Saint Marys Hospital female patients will have pregnancy test, unless clinically determined to not be able to become pregnant.

9.7. Visit-2 First EMU study visit

Baseline characterization of sleep and perturbations

Baseline day:

Upon the first day of their arrival to Saint Marys Hospital, patients will be familiarized with the testing battery and EEG equipment. We will run the battery of questionnaires and tests while participants are on their usual stimulation parameters and medications, to ensure that delays/errors when this is repeated upon awakening are not a result of task novelty.

Based on each patient’s sleep diary and actigraphy from their Empatica watch, we will determine a bedtime that corresponds with their usual schedule. The gold standard polysomnography will be used to measure scalp EEG and sleep over two nights in each participant. One night will be used to characterize a patient’s sleep state with their typical therapy parameter settings (stimulation on) or off stimulation, while during the other night effects of defined perturbations (examples outlined in Figures 1-5 in the Appendix) on sleep we be assessed. Medications and other influences will be controlled as much as possible between the control and the experiment (i.e. consistent with their daily medication dose). Patients will be under supervision of trained clinical personnel.

For these two nights, we will configure each subject with the polysomnography system and programmer. This will provide a consistent environment over both nights.

Baseline night: The main purpose of this first night of recording is for the researcher to become familiar with the patient's typical sleep patterning /sleep stages and their electrophysiological and polysomnographic correlates. For this we will capture and quantify the EEG in different stages (WAKE, N1, N2, N3, REM) and observe respiratory and autonomic parameters. Should we be able to recruit patients with DBS devices that enable us to sample intracranial data, we will also record samples of data during different sleep stages.

At the end of the night, we will define the dominant EEG characteristics for each sleep stage and translate this to transition models for each patient. The outcome of this analysis will be used to generate the patient-specific stimulation perturbations based on sleep stages. Data collected during the first (baseline) night will be used as the baseline for the remainder of the protocol.

Upon awakening (at a time decided based on the sleep diary), a salivary sample will be obtained for morning cortisol. Participants will complete specific tasks at the time of awaking, and again at 30 minutes and 60 minutes post awaking.. These tasks will consist of the KSS, Mood, KDT, , , and PVT.

During the intervening day, the patients will be allowed to read, watch television, and socialize with caregivers, as well as complete tasks and questionnaires.

Testing/stimulation night:

We will use the programmers in an initial open-loop approach during the first visit, to see if a pattern can help optimize sleep stages and perturb sleep patterns. We will reconfigure each subject with polysomnography system and ensure it is still operating per requirements. The intent is to provide a consistent environment over both nights. We will again capture EEG (and if available, intracranial data). We will use real-time classification of sleep architecture to perturb the networks with variants of stimulation (see tables per target in Appendix A). For the initial sleep cycles, we will be using manual (open loop) interventions by the sleep monitor and the site clinician and scientist. In parallel, the laptop algorithm will be running a prototype closed-loop control to demonstrate the bridge to automated closed loop control. The output of the algorithm and stimulation commands will be logged and compared to the manual interventions.

Upon waking, a salivary sample will be obtained for measuring of early morning cortisol. The cognitive tasks will be performed as listed previously, to assess sleep inertia and other response variables. Subjective questionnaires will be administered post-cognitive screen. Cognitive tests will continue throughout the day to assess variation in the patient's performance.

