7. STUDY DESIGN

This is a feasibility study that will take place in Mayo Clinic Rochester, MN. A parallel study will also be conducted at a UK site (Oxford University, UK) and University of California San Francisco (UCSF) under the same funding but this will be reviewed by their local IRB. Anonymized data will be shared between sites for analyses purposes.

Participants will be identified during their routine clinic visits and care and invited to participate in the study. Screening of interested potential participants will take into account pre-operative assessment data.

Testing will ensue (within a variable period from screening, but within the study timeline), over two visits to the epilepsy monitoring unit in Saint Marys Hospital (SMH), each consisting of two nights. Baseline sleep recordings will be obtained over the first night of the first visit, with the remaining nights consisting of stimulation trials. Questionnaires, daytime vigilance testing, autonomic parameters and cortisol levels will be collected as described in the sections to follow. No long-term follow-up is planned at this stage.

With regards to data collection processes, our population of patients have already been implanted with a DBS system (such as an FDA approved Medtronic Activa PC, Boston Scientific Vercise, Abbot Infinity systems). In addition, we will analyze data previously collected from patients with the RC+S Summit System under FDA-IDE G180224. The analysis of the RC+S data will be included in the FDA-IDE G180224 yearly submissions.

Note: A parallel study DBS devices currently under IDE investigations (such as Medtronic RC+S devices) will be pursued separately. Inclusion of patients with investigational devices under FDA investigational device exemptions will require prior approval from FDA.

We will leverage rules from the current AASM guidelines, technologies and methods for manual and automated sleep scoring using standard scalp polysomnography as well as novel methods we previously developed for sleep scoring using intracranial electrophysiology.

For perturbations, we will use the FDA approved clinician programmer and patient programmer. In this study, we specify as high frequency (HF) a stimulation range from 40 Hz to 250 Hz, while low frequency (LF) will be defined as 2 Hz to 40 Hz. All perturbations will be within the clinical range used and approved for DBS patients.

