11.3. Sample Size Determination

This is a feasibility study into recruiting and conducting the study procedures in patient populations. Given the exploratory and novel nature of this study, effect sizes are as of now, unknown. We are collecting from different groups bearing in mind that a minimum n=3 is required for the most rudimentary statistics based on patient number. We therefore expect 15 patients to be the lowest bound for 5 different DBS electrode locations. There will be multiple comparable stimulation epochs per patient, across three nights (second night of first visit and both nights of second visit). The number of sleep stages and cycles per night will vary between participants, with an added unknown being the effect of the disease state on sleep. However, this within- and across-subject comparison will boost statistical power. Further support that an N-of-1 trial design can be used for closed-loop DBS research and provide individualized, precision data to inform device development, was published recently (Stevens and Gilbert 2020).

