11.5. Decision points

As specified in section 9.7., interim analyses of each patient's baseline data will be performed after the first night of the first visit. This will help establish a familiarity with each participant's sleep stage duration and EEG morphology, their maximum sleep depth as well as the presence of pathological sleep features. Based on this knowledge, decisions on the timing of the stimulation during the second night will be made by the PI and sleep scientist team, as well as basic assumptions on the desired effects. Following the first visit, further interim analyses will determine to what degree these assumptions were correct, so that stimulation patterns can be explored further during the second visit.

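### Night 1 helps set each patient's stimulation target and is also the baseline, so a metric targeted for its night-1 value can appear improved through regression to the mean

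*Combined protocol and SAP*

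**What the plan says.** Section 7 plans one baseline night: "Baseline sleep recordings will be obtained over the first night of the first visit, with the remaining nights consisting of stimulation trials".

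Section 9.7 says of the night-1 analysis that "The outcome of this analysis will be used to generate the patient-specific stimulation perturbations based on sleep stages". The next sentence adds: "Data collected during the first (baseline) night will be used as the baseline for the remainder of the protocol".

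Under Section 11.5 the night-1 review covers stage durations, EEG form, "their maximum sleep depth as well as the presence of pathological sleep features". It informs the timing of stimulation on the second night, "as well as basic assumptions on the desired effects". Then: "Following the first visit, further interim analyses will determine to what degree these assumptions were correct". The comparator for that check is not named.

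Section 9.8 compares recordings made at the start of both Visit-3 nights with the baseline. It also plans an adaptive night and a control night. The control night is open loop or off and is guided by first-visit data. Section 9.6.2 adds contrasts of OFF with ON configurations and of one pattern with another.

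There is no blinding (Section 9.5). Nothing in Section 11 adjusts for selection on a baseline value or asks for targets to be recorded in advance.

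**The concern.** A value that stands out on a single night is partly a stable trait of the patient and partly that night's chance. The chance part does not recur. If the team sees a short N3 or a poor sleep efficiency on night 1, aims to improve it, and measures the result as change from night 1, some improvement is expected whatever the stimulation does. This follows from selecting on the baseline value. It would remain even if the nights were fully exchangeable, so it is distinct from any order or adaptation effect.

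The exposure matters most for whole-night measures. The secondary outcomes in Section 6 include sleep and REM latency, stage durations, number of awakenings and sleep efficiency. These cannot be divided into ON and OFF epochs within a night, so they need another night as reference, and at the first visit night 1 is the only one available. A mistaken finding that the assumptions were correct would carry forward, because Section 9.8 bases the second visit largely on first-visit results.

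**Working it through.** **The plan's own figure.** The only sample-size derivation is in Section 11.3: 3 patients per location × 5 locations = 15, which reproduces. The plan gives no effect size, night-to-night reliability, numeric significance level or figure for regression to the mean, so what follows is an illustration.

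**Inputs.** From the documents: n = 15 in total, at least 3 per location, one baseline night. Assumed:
- No true stimulation effect.
- Metrics standardised to SD 1 on a single night.
- Night-to-night ICC 0.3, 0.5 or 0.7.
- Four candidate metrics, with the one that looks worst on night 1 targeted.
- Between-metric correlation ρ of 0 or 0.5, the same in the stable and the nightly parts.
- A paired t test, two-sided at 0.05.

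**Expected apparent gain.** The lowest of four independent standard normals lies on average 1.03 SD below the mean, and correlation shrinks that distance by √(1 − ρ). On the next night the expected deficit is only ICC times as large. So

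gain = (1 − ICC) × √(1 − ρ) × 1.03.

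- ρ = 0: 0.7 × 1.03 = 0.72 SD; 0.5 × 1.03 = 0.52 SD; 0.3 × 1.03 = 0.31 SD.
- ρ = 0.5, so √0.5 = 0.707: 0.7 × 0.707 × 1.03 = 0.51 SD; 0.36 SD; 0.22 SD.

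If the target is fixed without looking at its value, the expected starting deficit is zero and so is the gain. Using the same night for both purposes is therefore not enough to create bias; selection on the value is also needed.

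**False-positive rates by simulation, no true effect:**

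| Case | ICC 0.3 | ICC 0.5 | ICC 0.7 |
|---|---|---|---|
| n = 15, worst of 4, independent metrics | 68% | 51% | 32% |
| n = 15, worst of 4, ρ = 0.5 | 37% | 27% | 18% |
| n = 15, worst of 2, independent metrics | 25% | 19% | 13% |

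In the first row 75%, 71% and 66% of patients appear improved, where 50% is expected by chance.

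**Variations at ICC 0.5, four metrics:**
- ρ = 0.8, n = 15: about 14%.
- ρ = 0.5, n = 15, half the targets chosen for reasons unrelated to the night-1 value: about 10%.
- No selection on the value, n = 15: 5%.
- Independent metrics, n = 3: about 9%.

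When the reference is a separate night in the baseline condition that played no part in choosing the target, the rate returns to 5% and the mean change to zero.

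**Baseline-adjusted analysis.** For each metric, regress the later-night value on its night-1 value and an indicator that this metric was targeted in that patient. With n = 15, four metrics and ICC 0.5, null rejection is about 5%, so the test is valid. But 15 / 4 gives about four targeted patients per metric, and power for a true 0.8 SD effect is only about 19%.

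**The case against.** The strongest reply is that the documents never say a target is picked because its night-1 value was extreme. In Section 9.7 the analysis that feeds the perturbations defines each stage's dominant EEG features and a transition model, that is, how to recognise the stages in this patient. Section 11.5 speaks first of timing. The examples in Appendix A are keyed to sleep stage, not to a patient's deficit. All of that stands. A reader might infer that the double use of night 1 by itself inflates the results, or that the plan commits the team to chasing each patient's worst metric. The documents support neither.

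A reader might also take it as stated that the Section 11.5 check is made against night 1. The general baseline sentence in Section 9.7 makes that likely, but it remains an inference.

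Nor is every effect claim exposed. The ON versus OFF and pattern-versus-pattern contrasts (Section 9.6.2) and the adaptive versus control contrast (Section 9.8) do not use night-1 values.

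Finally, 68 to 32% is not the study's false-positive rate. No pooled paired t test is planned, and sleep metrics overlap by construction: total sleep time is the numerator of sleep efficiency, and the stage durations add up to it. That is why the correlated and partial-selection cases belong beside it.

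What the reply does not remove is this. Section 11.5 links the desired effects to what was seen on night 1, including pathological features, and Section 5 aims to tailor stimulation so as to optimise sleep. Targeting an apparent deficit is therefore plausible. With no recorded rule, nobody could later show that it did not happen. The Visit-3 control night is not guaranteed to repeat the baseline condition.

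**Conclusion.** The point holds as a conditional risk. For any metric targeted because of its night-1 value, change from night 1 is biased towards apparent success, and the plan neither prevents this nor allows it to be checked afterwards. The exposure is limited to later-night versus night-1 contrasts, chiefly whole-night measures.

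Under the stated assumptions the false-positive rate at n = 15 runs from 5% with no selection on the value, through about 10% with partial selection and correlated metrics, to 37–18% with full selection at correlation 0.5, and 68–32% with full selection and independent metrics. ICC, number of candidate metrics, their correlation and the share of deficit-based targets are all assumptions, since the documents give none of them. For an exploratory feasibility study this does not undermine the design, but it should be corrected because the remedy is cheap.

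**What to change.** 1. In Section 11.5, require that each patient's targeted metric, the intended direction and the reason for choosing it are recorded before night 2.
2. In Sections 11.2 and 11.5, state that a targeted metric will not be judged by raw change from night 1. Base effect claims on planned contrasts that do not use night 1: ON versus OFF epochs, adaptive versus control night, or the Visit-3 control night as reference in those patients where it is run in the baseline condition. Report night-1 change on targeted metrics as descriptive and subject to regression to the mean, and name the comparator for the Section 11.5 check.
3. Optionally report the baseline-adjusted ANCOVA with a targeted indicator as a supporting analysis.

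The cost is analysis wording and one short CRF entry per patient, with no extra night. The downsides are fewer and less favourable claims from the first visit, a Visit-3 reference available only for some patients, and low precision for the ANCOVA (the 19% power shown above), so it cannot carry the main conclusion.

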2. LAY SUMMARY

Treatment of sleep disturbances is mainly attempted through behavioral modifications or drug administration. However, behavioral approaches may fail, and certain drugs are associated with unwanted side effects or residual effects upon awakening (e.g. sleepiness, ataxia) which can increase the risks of falls and fractures. In addition, there can be systemic consequences of long-term medication use. An alternative method of manipulating sleep is by electrically stimulating the brain to directly influence the brain circuits underlying behavioural state. To date, there have been mixed results from stimulating superficial areas of the brain and, as far as we know, there has been no systematic attempt to influence deep brain activity using deep brain stimulation.

Many patients suffering from neurological diseases, such as Parkinson's Disease (PD), Multiple Systems Atrophy (MSA), Essential Tremor, Chronic Pain, and Epilepsy also have disrupted sleep. Currently, at stages where drug treatment do not offer adequate control of their primary neurological symptoms, these patients are implanted with a deep brain stimulation (DBS) system. This involves depth electrodes implanted into specific brain locations to deliver electrical stimulation to the targeted area..

The aim of this feasibility study is to investigate whether we can improve sleep quality in patients who have DBS devices implanted for existing neurological indications by delivering targeted stimulation patterns during specific stages of sleep using their existing DBS device. We will only use electrical stimulation frequencies that have been proven to be safe for patients. We will perform these studies in patients admitted to the hospital in order to examine the structure and quality of sleep as well as how alert patients are when they wake up, while also monitoring physiological markers such as brainwave activity, heart rate and blood pressure. Upon awakening, we will ask the patients to provide their subjective opinion of their sleep and complete some simple tests to see how alert they are compared to a night of no electrical stimulation.

We hope that our study will open new ways of optimizing sleep in patients with neurological disease who are implanted with DBS devices. We also believe that our findings will broaden the understanding of how the activity of deep brain areas influences sleep and alertness.

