Interventions	Open and closed-loop electrical modulation triggered and based on ongoing sleep staging by researcher as well as automated closed-loop algorithm for stimulation.	Effect on autonomic measures such as heart-rate variability and blood pressure, as well as salivary cortisol levels	
 On awakening (post-baseline night and post-intervention) During day (post-baseline & intervention) Salivary cortisol levels measured on awakening each day (6am).
Comparator	Within-subject: their usual stimulation settings (stimulation at high/low frequency, as per established practice) Between-subject: different nuclei (stimulation sites)		

4.

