6. OBJECTIVES AND OUTCOME MEASURES

Objectives	Outcome Measures	Timepoint(s) of outcome measure
Primary Objectives		
Feasibility of study	Ability to recruit planned participant number and carry out scheduled experiments in reproducible fashion	
 Analyses post-study completion Some evidence during interim analyses per group
Effect of stimulation on sleep stages	EEG changes (frequency changes, changes in EEG patterns and sleep structure)	
 During stimulation Post-stimulation at specific sleep stages

Secondary Objectives
 
Effect of stimulation on sleep inertia and vigilance & performance during the day
 
Controlling sleep depth and sleep-wake transitions
	
Performance on short and long test battery (see section 9.6.3)
 
Assessment of effect on latency to sleep onset and REM sleep, number of sleep cycles, duration of sleep stages, number of awakenings per night, sleep efficiency
	
 Upon awakening (post-baseline night and post-intervention) During the day (post-baseline and intervention) During intervention nights

Tertiary Objectives
 
Effect of stimulation on other measures of arousal
	
Effect on autonomic measures such as heart-rate variability and blood pressure, as well as salivary cortisol levels
	
 Overnight measurements Salivary cortisol levels measured upon awakening each day (6am).

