9.6.2. Description of comparator(s)

We will use both within- and between-subject comparators. As within-subject comparators, these will primarily be the usual patient settings of low frequency (LF) or high frequency (HF) continuous stimulation (ON) at the clinically prescribed amplitude and frequency. Therefore, we will be able to make assumptions both about these settings (beneficial/disruptive) and the intervention, with regards to effects on EEG patterns, autonomic activity, behavioural measures etc. In addition, since we will be applying a number of exploratory patterns per night (according to sleep stage), each of these will be used as a comparator to others. Where electrical stimulation will be switched off (OFF), this will be compared to individual stimulation configurations as well as all (ON) states. Where comparable stimulation patterns will be used in different patient groups (e.g. HF stimulation during NREMS2 in both HC and ANT), these will serve as between-subject comparators. In addition, given the exploratory nature of this study, the responses of different participants to the same stimulation pattern will be compared (e.g. effects on sleep stages/EEG rhythms of stimulation during REM, between patients with hippocampal electrodes).

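### Night 1 is always the baseline, so whole-night and next-morning contrasts with it mix stimulation with night order (and, for Visit 3, with visit); the control condition also needs reconciling

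*Combined protocol and SAP*

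**What the plan says.** **Position and use of the baseline night.** Section 7 fixes the sequence: "Baseline sleep recordings will be obtained over the first night of the first visit, with the remaining nights consisting of stimulation trials". Section 9.7 makes that night the reference for everything after it: "Data collected during the first (baseline) night will be used as the baseline for the remainder of the protocol". The second night of the first visit is always the open-loop testing night. Section 9.8 gives the second hospital visit (Visit 3) an adaptive night and a control night, and states no order for them.

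**Outcomes that depend on it.** Section 6 times the secondary test batteries at "Upon awakening (post-baseline night and post-intervention"), so the morning after night 1 is set against later mornings. Cortisol is taken once each morning. For the sleep-architecture measures (latencies, cycles, stage durations, awakenings, efficiency), section 6 names only intervention nights; their link to night 1 comes from 9.7.

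**Control condition.** The lay summary refers to "simple tests to see how alert they are compared to a night of no electrical stimulation". The Synopsis gives "Within-subject: their usual stimulation settings". Section 9.6.2 says of the within-subject comparators that "these will primarily be the usual patient settings of low frequency (LF) or high frequency (HF) continuous stimulation (ON"), and adds: "Where electrical stimulation will be switched off (OFF), this will be compared to individual stimulation configurations as well as all (ON) states". Section 9.7 allows the characterisation night to be on usual therapy or off. Section 9.8 allows the control night to be open loop or off.

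**Analysis.** Section 11.2 names general methods, with no night or visit term. It falls back on consistency and trends where testing is not possible.

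**The concern.** The reference night always comes first and the stimulation nights always come later. If patients sleep better, or test better on waking, simply because they have become used to the unit and the recording equipment, that change has the same sign in every patient and appears as a stimulation effect. Recruiting more patients narrows the interval around the wrong quantity. At stake are the secondary objectives (sleep inertia, sleep depth and sleep-wake transitions) and tertiary cortisol, and possibly part of the primary objective on sleep stages.

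The control wording is a second, separate matter. If one patient's reference is usual stimulation and another's is off, a night-to-night contrast has no single meaning.

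**Working it through.** **1. The plan's own figure.** Section 11.3 derives its lower bound as 3 patients × 5 electrode locations = 15, which reproduces. There is no power calculation, no numerical alpha and no assumed effect; 11.3 says effect sizes are unknown.

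**2. What each contrast can separate.** Take the nights in order as baseline (B), open loop (O), then adaptive (A) and control (C), with patient effects and a free effect for each night.
- O − B: both nights fall in one visit. The contrast is confounded with night order, not with visit.
- A − B and C − B: confounded with night order and with visit.
- A − C: not estimable if all patients have the same Visit-3 order; estimable if the order varies between patients.
- With Visit-3 order varied, O − B still cannot be estimated with free night effects, and neither can A − B when the control differs from the baseline condition.

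A rank check of the design matrix confirms each line.

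**3. Within-night comparisons.** Two patterns compared on the same night do not use night 1. However, in the first Appendix A example N3 on night 2 appears only under low-frequency stimulation, and in the second REM appears only under high-frequency stimulation. Neither shows a same-stage comparator for that cell within the night; the one displayed is night 1 on standard settings. Some stage-specific EEG contrasts may therefore also rest on night 1.

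**4. Illustrative size.** Assumed, not in the documents: no stimulation effect, normal errors, a pooled paired t test at two-sided 0.05, and a shift δ from night 1 to the later night in single-night SD units. With between-night correlation ρ, the SD of the paired difference is √(2(1 − ρ)), and the noncentrality is δ√n / √(2(1 − ρ)).

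For n = 15 (14 df, critical t 2.145):

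| δ | ρ = 0: noncentrality | false positives | ρ = 0.5: noncentrality | false positives |
|---|---|---|---|---|
| 0.3 | 0.822 | 12% | 1.162 | 19% |
| 0.5 | 1.369 | 25% | 1.936 | 44% |
| 0.8 | 2.191 | 53% | 3.098 | 82% |

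The ρ = 0.5 columns apply if the SD is read as total SD. At n = 3 with ρ = 0 the rates are 6%, 7% and 9%. They are low because a test on three patients detects little of anything, bias included.

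**5. What randomising the Visit-3 order would give.** Form adaptive minus control in each patient, average within each order group, and take the mean of the two group averages. A constant shift between the two nights then cancels. In simulation the false-positive rate stays at 5% under shifts of 0.3, 0.5 and 0.8, with no carry-over. With a 7/8 split and ρ = 0, the SE is 0.5 × √2 × √(1/7 + 1/8) = 0.366 single-night SD, on 13 df (critical t 2.160). For true effects of 0.3, 0.5 and 0.8 single-night SD the noncentralities are 0.820, 1.366 and 2.186, and power is 0.118, 0.245 and 0.525. With three patients in one target (2/1 split) there is 1 df and the critical t is 12.7.

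**6. Control wording side by side.** Section 9.6.2 makes usual settings the main comparator and also uses off periods, so it accommodates the Synopsis and both options in 9.7. Appendix A is headed as an example. Sections 7 and 11.3 count both Visit-3 nights as stimulation nights, which fits 9.8 if the control is open loop. What remains unreconciled is the lay summary's no-stimulation night against usual settings in the Synopsis and 9.6.2, and the absence of a rule for the off option in 9.7 and 9.8.

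**The case against.** The strongest reply has five parts.

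- **Night 1 has to come first.** It generates the patient-specific perturbations (9.7, 11.5). This stands, and nothing here proposes moving it.
- **There are safeguards.** Patients practise the battery and meet the EEG equipment beforehand, bedtime is matched to habit and the environment is kept constant. On the watch, 9.6.3 says: "These signals will be used to assess how the patient is sleeping prior to the admissions to the hospital". The recordings at the start of each Visit-3 night, if made before perturbation, give a partial check on drift between visits. These reduce the problem. None of them separates adaptation to the unit from stimulation in an outcome with one value per night or morning.
- **It is an unblinded, exploratory feasibility study, and the plan contains no pooled between-night test.** This is true, so the percentages show a mechanism and do not measure harm in this trial. The effect on sleep stages is still a primary objective, and section 11.2 intends to look for statistical significance.
- **The control wordings are mostly compatible.** Largely accepted. A reader might infer that every section names a different control; the documents do not support that, and only the narrower conflict above remains.
- **The remedy answers a different question.** Adaptive versus control is not stimulation versus usual settings, and it could be null even if both modes help. This stands, which is why the contrast is not put forward as the study's main one.

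**Conclusion.** The concern holds in this limited form, and the change is worth making because it is cheap. Whole-night and next-morning contrasts with night 1 cannot separate stimulation from night order, and for Visit-3 nights from visit as well. The structural point needs no assumed numbers. Its size is unknown: the 12% to 53% range at n = 15 (19% to 82% at a between-night correlation of 0.5) rests on assumed shifts and an assumed test.

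Three stronger readings are tempting and should be resisted:
- That every later night is confounded with visit. Night 2 is in the same visit as night 1.
- That within-night comparisons leave the primary EEG outcome untouched. The Appendix A examples do not show this for every stage. Nor do they show that it fails throughout, since separate epochs of one stage could supply a comparator.
- That the comparison of control nights in 11.2 certainly mixes conditions. This follows only if those nights are night 1 and the Visit-3 control night; the sentence can also be read as a comparison across patients.

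Confidence is medium, because the Appendix B schedule and the figures cited in 9.7 were not available and could bear on night order.

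**What to change.** 1. In 9.8, randomise each patient's order of the adaptive and control nights. Both draw on first-visit data, so either can come first. In 11.2, include night order when these two nights are compared, pooled across targets, and keep per-target results at n = 3 descriptive. State that the contrast estimates adaptive against whatever the control is, and that at n = 15 its power is only about 12%, 25% and 53% for effects of 0.3, 0.5 and 0.8 single-night SD (independent nights).
2. In 11.2, label whole-night and next-morning contrasts with night 1 as descriptive, and say that the confounding remains.
3. Reconcile the lay summary, the Synopsis, 9.6.2, 9.7 and 9.8 on the control condition, including when the off option applies. The choice is the sponsor's. If the control nights in 11.2 are night 1 and the Visit-3 control night, and they need not share a condition, requalify the variability sentence.

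The cost is a randomisation list and some wording, with no added nights or patients. The downsides are less freedom in scheduling the Visit-3 nights, an assumption of no carry-over between adjacent nights, and a pooled estimate that averages over different targets and patterns.
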